Percentages are calculated out of the number of participants ^aIn the safety population ^bSometimes took/sometimes left the rings ^cLeft rings at the research centre

^dWith main partner ^eTook rings ^fUsed a condom ^gHad anal sex since last visit ^hHad a menstrual bleeding/spotting since last visit

ⁱHad ring expelled/removed since last visit ^jCleaned ring before reinsertion ^kInserted fingers into vagina

Table 14.6.9
 Participant Questionnaire – Last Product Use Visit
 Safety Population

Trial Month X	Statistic	IPM 032 Overall (N=XXX)
Products used in the past 3 months to control menstrual bleeding/spotting		
Tissue, toilet paper, paper, cloth or cotton wool put inside the vagina	n (%) ^h	X (X.X)
Tissue, toilet paper, paper, cloth or cotton wool put inside the underwear/clothing	n (%) ^h	X (X.X)
Tampon	n (%) ^h	X (X.X)
Sanitary pad	n (%) ^h	X (X.X)
Menstrual cup	n (%) ^h	X (X.X)
Water without soap (inside the vagina)	n (%) ^h	X (X.X)
Water with soap (inside the vagina)	n (%) ^h	X (X.X)
Nothing was used	n (%) ^h	X (X.X)
Other	n (%) ^h	X (X.X)
Ring removed/expelled since last scheduled visit?		
Yes	n (%) ^a	X (X.X)
No	n (%) ^a	X (X.X)
Reason why the ring was removed/expelled		
Took it out because it was uncomfortable/painful	n (%) ⁱ	X (X.X)
Took it out to clean the ring	n (%) ⁱ	X (X.X)
Took it out because on menses	n (%) ⁱ	X (X.X)
Took it out because of real/perceived side effects	n (%) ⁱ	X (X.X)
Took it out because partner requested it	n (%) ⁱ	X (X.X)
Took it out for sex	n (%) ⁱ	X (X.X)
Took it out so that partner did not find out about it	n (%) ⁱ	X (X.X)
Accidentally came out	n (%) ⁱ	X (X.X)
Other	n (%) ⁱ	X (X.X)
When the ring was removed/expelled did you clean the ring before reinsertion?		
Yes	n (%) ⁱ	X (X.X)
No	n (%) ⁱ	X (X.X)

Programmers Note: Please add in 'Chose not to answer' where applicable

Percentages are calculated out of the number of participants ^aIn the safety population ^b Sometimes took/sometimes left the rings ^c Left rings at the research centre

^d With main partner ^e Took rings ^f Used a condom ^g Had anal sex since last visit ^h Had a menstrual bleeding/spotting since last visit

ⁱ Had ring expelled/removed since last visit ^j Cleaned ring before reinsertion ^k Inserted fingers into vagina

Table 14.6.9
 Participant Questionnaire – Last Product Use Visit
 Safety Population

Trial Month X	Statistic	IPM 032 Overall (N=XXX)
What did you use to clean the ring when it was removed/expelled?		
Water only	n (%) ^j	X (X.X)
Soap only	n (%) ^j	X (X.X)
Water and soap	n (%) ^j	X (X.X)
Disinfectant	n (%) ^j	X (X.X)
Water and soap	n (%) ^j	X (X.X)
Disinfectant	n (%) ^j	X (X.X)
Herbal products	n (%) ^j	X (X.X)
Traditional medicine	n (%) ^j	X (X.X)
Bubble bath	n (%) ^j	X (X.X)
Bath salts	n (%) ^j	X (X.X)
Dishwashing liquid	n (%) ^j	X (X.X)
Other	n (%) ^j	X (X.X)
Level of being worried about getting infected with HIV in the next year		
Very worried	n (%) ^a	X (X.X)
A little worried	n (%) ^a	X (X.X)
Not worried at all	n (%) ^a	X (X.X)
Inserted fingers into vagina since last schedule visit		
Yes	n (%) ^a	X (X.X)
No	n (%) ^a	X (X.X)
Reason for inserting fingers into vagina		
Check the position of the ring	n (%) ^k	X (X.X)
Insert/remove the ring	n (%) ^k	X (X.X)
Cleaning	n (%) ^k	X (X.X)
Sexual pleasure	n (%) ^k	X (X.X)
Insert a product for the management of menses	n (%) ^k	X (X.X)
Other	n (%) ^k	X (X.X)

Programmers Note: Please add in 'Chose not to answer' where applicable

Percentages are calculated out of the number of participants ^aIn the safety population ^b Sometimes took/sometimes left the rings ^c Left rings at the research centre
^d With main partner ^e Took rings ^f Used a condom ^g Had anal sex since last visit ^h Had a menstrual bleeding/spotting since last visit
ⁱ Had ring expelled/removed since last visit ^j Cleaned ring before reinsertion ^k Inserted fingers into vagina

Table 14.6.9
 Participant Questionnaire – Last Product Use Visit
 Safety Population

Trial Month X	Statistic	IPM 032 Overall (N=XXX)
Participant views on are the following good ways to ensure ring use: Adherence		
Test blood to see how much medicine is in the blood		
Yes	n (%) ^a	X (X.X)
No	n (%) ^a	X (X.X)
Test used ring to see how much medicine is still in the ring		
Yes	n (%) ^a	X (X.X)
No	n (%) ^a	X (X.X)
Ask the woman if she has been using the ring		
Yes	n (%) ^a	X (X.X)
No	n (%) ^a	X (X.X)
Other		
Yes	n (%) ^a	X (X.X)
No	n (%) ^a	X (X.X)
Would more women use the ring properly if they knew the blood tests/used rings would show staff who was using the ring as intended and who was not?		
Yes	n (%) ^a	X (X.X)
No	n (%) ^a	X (X.X)
Don't know	n (%) ^a	X (X.X)
Is it possible for women to use the ring as requested?		
Yes	n (%) ^a	X (X.X)
No	n (%) ^a	X (X.X)
Don't know	n (%) ^a	X (X.X)

Programmers Note: Please add in 'Chose not to answer' where applicable

Percentages are calculated out of the number of participants ^aIn the safety population ^b Sometimes took/sometimes left the rings ^c Left rings at the research centre

^d With main partner ^e Took rings ^f Used a condom ^g Had anal sex since last visit ^h Had a menstrual bleeding/spotting since last visit

ⁱ Had ring expelled/removed since last visit ^j Cleaned ring before reinsertion ^k Inserted fingers into vagina

Table 14.6.9
 Participant Questionnaire – Last Product Use Visit
 Safety Population

Trial Month X	Statistic	IPM 032 Overall (N=XXX)
Most likely reason(s) for women to remove the ring	n (%) ^a	X (X.X)
Partner request	n (%) ^a	X (X.X)
Fear of partner feeling it	n (%) ^a	X (X.X)
Influence of others (not partner)	n (%) ^a	X (X.X)
Wants a break from having the ring inside	n (%) ^a	X (X.X)
Menses	n (%) ^a	X (X.X)
Side effects	n (%) ^a	X (X.X)
Discomfort/pain	n (%) ^a	X (X.X)
Belief that ring doesn't work	n (%) ^a	X (X.X)
Other	n (%) ^a	X (X.X)
All women can use the ring without taking it out	n (%) ^a	X (X.X)
Strongly agree	n (%) ^a	X (X.X)
Somewhat agree	n (%) ^a	X (X.X)
Strongly disagree	n (%) ^a	X (X.X)
Women would need a break from using the ring every few months	n (%) ^a	X (X.X)
Strongly agree	n (%) ^a	X (X.X)
Somewhat agree	n (%) ^a	X (X.X)
Strongly disagree	n (%) ^a	X (X.X)
Would women in the community want to wear the ring if it were available?	n (%) ^a	X (X.X)
Yes	n (%) ^a	X (X.X)
No	n (%) ^a	X (X.X)
If the ring is made available to the public, where would most women want to get it from?	n (%) ^a	X (X.X)
A clinic	n (%) ^a	X (X.X)
Pharmacy	n (%) ^a	X (X.X)
Private doctor	n (%) ^a	X (X.X)
Other	n (%) ^a	X (X.X)
They wouldn't want to use it	n (%) ^a	X (X.X)

Programmers Note: Please add in 'Chose not to answer' where applicable

Percentages are calculated out of the number of participants ^aIn the safety population ^b Sometimes took/sometimes left the rings ^c Left rings at the research centre

^d With main partner ^e Took rings ^f Used a condom ^g Had anal sex since last visit ^h Had a menstrual bleeding/spotting since last visit

ⁱ Had ring expelled/removed since last visit ^j Cleaned ring before reinsertion ^k Inserted fingers into vagina

Table 14.6.9
 Participant Questionnaire – Last Product Use Visit
 Safety Population

Trial Month X	Statistic	IPM 032 Overall (N=XXX)
Willingness to pay for the ring, if it was to be made available to the public		
It should be free	n (%) ^a	X (X.X)
Would pay	n (%) ^a	X (X.X)
Spend South African Rand on ring	Mean (q1,med,q3) SD (Min, Max)	XX.X (XX.X,XX.X,XX.X) XX.XX (XX, XX)
Spend Ugandan Shilling on ring	Mean (q1,med,q3) SD (Min, Max)	XX.X (XX.X,XX.X,XX.X) XX.XX (XX, XX)
Where should the ring be marketed/advertised if it was to be made available to the public?		
By qualified healthcare providers	n (%) ^a	X (X.X)
The local clinic/hospital notice boards	n (%) ^a	X (X.X)
Pamphlets in clinics only	n (%) ^a	X (X.X)
Pamphlets in pharmacies/private doctor	n (%) ^a	X (X.X)
Pamphlets in public places	n (%) ^a	X (X.X)
Television and/or radio	n (%) ^a	X (X.X)
Billboards	n (%) ^a	X (X.X)
Other place	n (%) ^a	X (X.X)

Programmers Note: Please add in 'Chose not to answer' where applicable

Percentages are calculated out of the number of participants ^aIn the safety population ^bSometimes took/sometimes left the rings ^cLeft rings at the research centre

^dWith main partner ^eTook rings ^fUsed a condom ^gHad anal sex since last visit ^hHad a menstrual bleeding/spotting since last visit

ⁱHad ring expelled/removed since last visit ^jCleaned ring before reinsertion ^kInserted fingers into vagina

Table 14.6.10
Participant Questionnaire – Vaginal Practices
Safety Population

Trial Month X	Applied using			Removed Ring?		Reason for using product					
	Product Used	Hands	Cloth	Other	No	Yes	General Cleaning	Clean During Menses	Clean Before Sex	Clean After Sex	...
External cleaning											
Water only	X (X.X)	X (X.X)	X (X.X)	X (X.X)	X (X.X)	X (X.X)	X (X.X)	X (X.X)	X (X.X)	...	X (X.X)
Soap only	X (X.X)	X (X.X)	X (X.X)	X (X.X)	X (X.X)	X (X.X)	X (X.X)	X (X.X)	X (X.X)	...	X (X.X)
Soap and Water	X (X.X)	X (X.X)	X (X.X)	X (X.X)	X (X.X)	X (X.X)	X (X.X)	X (X.X)	X (X.X)	...	X (X.X)
Disinfectant/ detergent	X (X.X)	X (X.X)	X (X.X)	X (X.X)	X (X.X)	X (X.X)	X (X.X)	X (X.X)	X (X.X)	...	X (X.X)
Traditional products	X (X.X)	X (X.X)	X (X.X)	X (X.X)	X (X.X)	X (X.X)	X (X.X)	X (X.X)	X (X.X)	...	X (X.X)
Other	X (X.X)	X (X.X)	X (X.X)	X (X.X)	X (X.X)	X (X.X)	X (X.X)	X (X.X)	X (X.X)	...	X (X.X)
Internal cleaning											
Water only	X (X.X)	X (X.X)	X (X.X)	X (X.X)	X (X.X)	X (X.X)	X (X.X)	X (X.X)	X (X.X)	...	X (X.X)
Soap only	X (X.X)	X (X.X)	X (X.X)	X (X.X)	X (X.X)	X (X.X)	X (X.X)	X (X.X)	X (X.X)	...	X (X.X)
Soap and Water	X (X.X)	X (X.X)	X (X.X)	X (X.X)	X (X.X)	X (X.X)	X (X.X)	X (X.X)	X (X.X)	...	X (X.X)
Disinfectant/ detergent	X (X.X)	X (X.X)	X (X.X)	X (X.X)	X (X.X)	X (X.X)	X (X.X)	X (X.X)	X (X.X)	...	X (X.X)
Traditional products	X (X.X)	X (X.X)	X (X.X)	X (X.X)	X (X.X)	X (X.X)	X (X.X)	X (X.X)	X (X.X)	...	X (X.X)
Gels	X (X.X)	X (X.X)	X (X.X)	X (X.X)	X (X.X)	X (X.X)	X (X.X)	X (X.X)	X (X.X)	...	X (X.X)
Other	X (X.X)	X (X.X)	X (X.X)	X (X.X)	X (X.X)	X (X.X)	X (X.X)	X (X.X)	X (X.X)	...	X (X.X)
Vaginal steaming											
Traditional products	X (X.X)	X (X.X)	X (X.X)	X (X.X)	X (X.X)	X (X.X)	X (X.X)	X (X.X)	X (X.X)	...	X (X.X)
Commercial products	X (X.X)	X (X.X)	X (X.X)	X (X.X)	X (X.X)	X (X.X)	X (X.X)	X (X.X)	X (X.X)	...	X (X.X)
Other	X (X.X)	X (X.X)	X (X.X)	X (X.X)	X (X.X)	X (X.X)	X (X.X)	X (X.X)	X (X.X)	...	X (X.X)

Programmers Note: Please repeat the table for all available Trial Months

Percentages are calculated out of the number of participants in the safety population

Table 14.6.10
Participant Questionnaire – Vaginal Practices
Safety Population

Trial Month X	Applied using			Removed Ring?		Reason for using product				
	Product Used	Hands	Cloth	Other	No	Yes	General Cleaning	Clean During Menses	Clean Before Sex	Clean After Sex
Inserted into vagina										
Tampon	X (X.X)	X (X.X)	X (X.X)	X (X.X)	X (X.X)	X (X.X)	X (X.X)	X (X.X)	X (X.X)	... X (X.X)
Cloth	X (X.X)	X (X.X)	X (X.X)	X (X.X)	X (X.X)	X (X.X)	X (X.X)	X (X.X)	X (X.X)	... X (X.X)
Paper	X (X.X)	X (X.X)	X (X.X)	X (X.X)	X (X.X)	X (X.X)	X (X.X)	X (X.X)	X (X.X)	... X (X.X)
Cotton wool	X (X.X)	X (X.X)	X (X.X)	X (X.X)	X (X.X)	X (X.X)	X (X.X)	X (X.X)	X (X.X)	... X (X.X)
Snuff/Kuber	X (X.X)	X (X.X)	X (X.X)	X (X.X)	X (X.X)	X (X.X)	X (X.X)	X (X.X)	X (X.X)	... X (X.X)
Zambuk	X (X.X)	X (X.X)	X (X.X)	X (X.X)	X (X.X)	X (X.X)	X (X.X)	X (X.X)	X (X.X)	... X (X.X)
Talc	X (X.X)	X (X.X)	X (X.X)	X (X.X)	X (X.X)	X (X.X)	X (X.X)	X (X.X)	X (X.X)	... X (X.X)
Other commercial products	X (X.X)	X (X.X)	X (X.X)	X (X.X)	X (X.X)	X (X.X)	X (X.X)	X (X.X)	X (X.X)	... X (X.X)
Traditional products	X (X.X)	X (X.X)	X (X.X)	X (X.X)	X (X.X)	X (X.X)	X (X.X)	X (X.X)	X (X.X)	... X (X.X)
Other	X (X.X)	X (X.X)	X (X.X)	X (X.X)	X (X.X)	X (X.X)	X (X.X)	X (X.X)	X (X.X)	... X (X.X)
External application of products										
Commercial cream	X (X.X)	X (X.X)	X (X.X)	X (X.X)	X (X.X)	X (X.X)	X (X.X)	X (X.X)	X (X.X)	... X (X.X)
Talc	X (X.X)	X (X.X)	X (X.X)	X (X.X)	X (X.X)	X (X.X)	X (X.X)	X (X.X)	X (X.X)	... X (X.X)
Intimate sprays	X (X.X)	X (X.X)	X (X.X)	X (X.X)	X (X.X)	X (X.X)	X (X.X)	X (X.X)	X (X.X)	... X (X.X)
Traditional products	X (X.X)	X (X.X)	X (X.X)	X (X.X)	X (X.X)	X (X.X)	X (X.X)	X (X.X)	X (X.X)	... X (X.X)
Other	X (X.X)	X (X.X)	X (X.X)	X (X.X)	X (X.X)	X (X.X)	X (X.X)	X (X.X)	X (X.X)	... X (X.X)

Programmers Note: Please repeat the table for all available Trial Months

Percentages are calculated out of the number of participants in the safety population

IPM 032

FIGURE SHELLS – VERSION 1.0, 26 MAR 2020

Number	Listing Heading
14.1	Demographics
14.1.1.1	Disposition of Participants
14.1.1.1.1	Time to Trial Discontinuation
14.1.1.1.2	Time to (Premature) Permanent Investigational Product Discontinuation
14.3	Safety Data
14.3.5.1	Adherence – Dapivirine Residual Levels in Used Rings
14.3.5.1.1	Dapivirine Ring Residual Levels (mg)
14.3.5.1.2	Dapivirine Ring Residual Levels (mg) By Trial Visit and Category of Residual Amount
14.3.5.1.3	Relating The Dapivirine Ring Residual Levels (mg) To The Time Intervals Between Consecutive Ring Replacements
14.3.5.1.4	Residual Levels of Dapivirine (mg) in The Last Three Returned Rings Prior To HIV Seroconversion VS Average Ring Residual Levels
14.3.5.1.8	Corrected Residual Levels of Dapivirine in The Last Three Returned Rings Prior To HIV Seroconversion VS Average Ring Residual Levels of HIV- Participants
14.3.7	Other Safety Data
14.3.7.7	Time to HIV-1 Seroconversion – m-ITT population
14.3.7.8	Time to HIV-1 Seroconversion – PP population
14.6	Other Data
14.6.4	Correlation Between Dapivirine Residual Amounts (mg) in Returned Used Vaginal Rings and Results From Visual Inspection of Returned Vaginal Rings

Figure 14.1.1.1.1
Kaplan-Meier Curves, Time to Trial Discontinuity
Safety Population

[figure not shown]
[figure not shown]

Figure 14.1.1.1.2
Kaplan-Meier Curves, Time to (Premature) Permanent Investigational Product Discontinuation
Safety Population

[figure not shown]
Programmers Note: Figure wil resemble F14.1.1.1 with time to permanent IP data.

Figure 14.3.5.1.1
Dapivirine Ring Residual Levels (mg)
Safety Population

[figure not shown]
Programmers Note: Please repeat for all centres.

Figure 14.3.5.1.2
 Dapivirine Ring Residual Levels (mg) By Trial Visit and Category of Residual Amount
 Safety Population

Programmers Note: Please repeat for all trial months.

Figure 14.3.5.1.3
 Relating The Dapivirine Ring Residual Levels (mg) To The Time Intervals Between Consecutive Ring Replacements
 Safety Population

Programmers Note: Please repeat for all centres.

Figure 14.3.5.1.4
Residual Levels of Dapivirine (mg) in The Last Three Returned Rings Prior To HIV Seroconversion VS Average Ring Residual Levels
Safety Population

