6.6 Data Presentations

Descriptive statistics will be presented overall and by research centre.

For continuous variables, the descriptive statistics will include, but not be limited to, mean and standard deviation (SD) (when appropriate), quartiles, range, and number of observations. For categorical variables, descriptive statistics may include frequencies, relative frequencies, and the number of observations.

Derived data where it is known in advance the result will be an integer (e.g. study day) will be presented with no decimal places. Means, medians and quartiles will be displayed to one more decimal place than the source data, dispersion statistics (e.g. standard deviation) will have two more decimal places, and the minimum and maximum will be displayed to the same number of decimal places as reported in the raw data. Percentages will be presented to one decimal place (excluding 0 and 100%). When appropriate, 95% confidence intervals will be presented.

The subsequent sections discuss the planned analyses beyond the listings and simple descriptive analyses.

Baseline is defined as the last available measurement before the first insertion of the IP. All visit dates will be calculated from the enrollment visit as baseline date.

Missing or partial dates will be imputed for AEs or concomitant medication dates. No other date imputations will be performed. For AEs or concomitant medication start dates, the following conventions will be applied:

2. If only the month and year are known, then the 15th of the month will be used (*i.e.* “15” will be imputed as the day of the month) unless the month and the year equal the month and the year of the first insertion of the ring. In such cases, the same day as the day of first ring insertion will be used (to ensure that the AE or concomitant medication is considered as treatment-emergent)
3. If only the year is known, then the first day of January will be used (*i.e.* “01JAN” will be imputed as the day and month) unless the year equals the year of first ring insertion, in which case the date will be imputed with the date of first ring insertion.

For concomitant medication end dates, the following conventions will be applied:

4. If only the month and the year are known, then the last day of the month will be used
5. If only the year is known, then the last day of December (i.e. "31DEC") or the date of trial completion/discontinuation will be used (whichever comes first).

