In instances where the date of IP initiation, *i.e.* the start date of ring use, is missing or unknown, the missing date will be imputed with the date of the enrollment visit.

In accordance with the protocol, each scheduled visit has a window period of \pm 7 days. If the participant does not return to the research centre for a scheduled visit prior to the start of the trial window of the next visit, the visit will be considered missed. If a participant presents for a visit outside the window for a scheduled trial visit, but prior to the start of the window for the next visit, it will be treated as a late visit. Missed visits and late visits will be documented as protocol deviations (refer to Section 7.2). Data recorded at late visits will be analysed as pertaining to the scheduled visit. Unscheduled visits may be performed at any time during the trial. If an unscheduled visit takes place within any given window period and any repeat observations are made within the given window period, the repeat values will be captured as pertaining to the unscheduled visit. Data from scheduled and unscheduled visits will be shown in the participant listings, and listings will be appropriately labelled when data arise from unscheduled visits. Data from scheduled visits will be presented in the summary tables.

Visit Schedule A will consist of participants who attend Trial Month Visits 1, 4, 7, 10, 13, and 16/Exit; Visit Schedule B will consist of participants who attend Trial Month Visits 1, 2, 5, 8, 11, 14, and 17/Exit; and Visit Schedule C will consist of participants who attend Trial Month Visits 1, 2, 3, 6, 9, 12, and 15/Exit.

Tables, figures, and listings of trial results will accompany the text of the CSR. Listings of all clinical data recorded in the CRFs will be provided, except for those CRFs which are used for administrative purposes, such as the Participant Encounter Form (PEN) and the End of Trial Inventory (ETI). Listings will be sorted by research centre and participant identification number (PID), and key variables such as visit date and/or trial visit number will be presented in each listing.

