10.1.1 Treatment Emergent Adverse Events (TEAEs)

TEAEs are defined as AEs which occurred/worsened after the first insertion of the IP, up to six weeks after last ring use.

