- **Table 14.7.10.2** will be similar to **Table 14.7.10.1** but the heading and analysis will be based on Any Timepoint

HIV-1 = Human immunodeficiency virus type 1; NNRTI = Non-nucleoside reverse transcriptase inhibitor ; NRTI = Nucleoside reverse transcriptase inhibitor; PI = Protease inhibitor
 Percentages are calculated out of the number of participants (per IPM 027 treatment) ^a In the virology population ^b Successful results

^c Resistance-associated mutations of interest not present in the data set are not included in the table

Resistance-associated mutations were defined using the Stanford HIV database algorithm Version 8.

Table 14.3.7.11
Data Overview of HIV-1 Seroconversion Timing Relative To HIV-1 RNA Detection and Treatment
Virology Population

Statistic	IPM 027 Dapivirine (N=XXX)	IPM 027 Placebo (N=XXX)	IPM 032 Overall (N=XXX)
First positive HIV-1 RNA Timing			
At time of seroconversion	n (%) ^a	X (X.X)	X (X.X)
Mutations detected before seroconversion	n (%) ^b	X (X.X)	X (X.X)
Mutations detected at seroconversion	n (%) ^b	X (X.X)	X (X.X)
Mutations detected after seroconversion	n (%) ^b	X (X.X)	X (X.X)
Before seroconversion			
At time of seroconversion	n (%) ^a	X (X.X)	X (X.X)
Mutations detected before seroconversion	n (%) ^b	X (X.X)	X (X.X)
Mutations detected at seroconversion	n (%) ^b	X (X.X)	X (X.X)
Mutations detected after seroconversion	n (%) ^b	X (X.X)	X (X.X)
Average days	Mean	XX.X	XX.X
Minimum and maximum days	(Min,Max)	(XX, XX)	(XX, XX)
IP use stopped			
At time of seroconversion	n (%) ^a	X (X.X)	X (X.X)
After seroconversion	n (%) ^a	X (X.X)	X (X.X)
Before seroconversion	n (%) ^a	X (X.X)	X (X.X)

Programmers Note: In case the date of last investigational product exposure (i.e. last ring removal) is missing, it is imputed with the last ring insertion date.

HIV-1 = Human immunodeficiency virus type 1

Percentages are calculated out of the number of participants (per IPM 027 treatment) ^a In the virology population ^b At the applicable visit

Table 14.3.7.12
 Overview of HIV-1 RNA and Genotyping Information Availability
 Virology Population

Statistic	IPM 027 Dapivirine (N=XXX)	IPM 027 Placebo (N=XXX)	IPM 032 Overall (N=XXX)
HIV-1 RNA for participants with HIV-1 seroconversion			
Participants with assessment prior to seroconversion	n (%) ^a	X (X.X)	X (X.X)
No HIV-1 RNA detected in any sample	n (%) ^b	X (X.X)	X (X.X)
HIV-1 RNA detected in at least 1 sample	n (%) ^b	X (X.X)	X (X.X)

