Centre Participant ID	Visit Date	IPM 027 Treatment	Date Inserted	Date Removed	Duration of Treatment	Scheduled Duration	Adherence Rate	Adherence Rate Category
Centre XX XXXXXXXXX	ddMMMyyyy	Dapivirine / Placebo	ddMMMyyyy	ddMMMyyyy	XX	XX	XXX	< 80% ≥ 80 to < 90% / ≥ 90%

Adherence rate = 100 x (Duration of Treatment / Scheduled Duration)

Missing or partial dates for when the ring was inserted or removed are treated as missing data during the calculation of the adherence rate

If a participant did not remember/know the date when a ring was expelled or removed, the number of days that the ring was out is counted as one day and applies to the ring that was dispensed during that time

Centre 01: Madibeng Centre for Research (MCR); Centre 02: MatCH Research Unit (MRU); Centre 04: Qhakaza Mbokodo (QM);

Centre 06: MRC/UVRI & LSHTM Uganda Research Unit (MRC/UVRI); Centre 07: Desmond Tutu HIV Foundation (DTHF), Masiphumelele; Centre 08: Ndlovu Care Group (NCG)

Listing 16.2.5.2
Self-Reported Acceptability and Adherence to Investigational Product
Safety Population

Centre Participant ID	Visit Date	Do You Think It Is Possible To Use Ring As Requested (i.e. Without Removing It)?	Do You Think Women In Your Community Would Like To Use This Ring If It Were Available?
Centre XX XXXXXXXX	ddMMMyyyy	Yes / No: XXXXXXXXXXXXXXXX / Don't know / Chose not to answer	Yes / No: XXXXXXXXXXXXXXXX / Chose not to answer

Adherence rate = $100 \times (\text{Duration of Treatment} / \text{Scheduled Duration})$

Missing or partial dates for when the ring was inserted or removed are treated as missing data during the calculation of the adherence rate

If a participant did not remember/know the date when a ring was expelled or removed, the number of days that the ring was out is counted as one day and applies to the ring that was dispensed during that time

Centre 01: Madibeng Centre for Research (MCR); Centre 02: MatCH Research Unit (MRU); Centre 04: Qhakaza Mbokodo (QM);

Centre 06: MRC/UVRI & LSHTM Uganda Research Unit (MRC/UVRI); Centre 07: Desmond Tutu HIV Foundation (DTHF), Masiphumelele; Centre 08: Ndlovu Care Group (NCG)

Listing 16.2.5.3
Returned Ring Log
Safety Population

Centre	Participant ID	Month of Ring Use	Replacement Ring	Shipped for Analysis	Shipped Date	Shared Results with Participant	Results Shared Date
XX	XXXXXXXXXX	XX	Yes / No	Yes / No	ddMMMyyyy	Yes / No	ddMMMyyyy

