4.4. Methods for Handling Missing Data

While every effort will be made to minimize the amount of missing data, as this is a retrospective analysis, some degree of missing data associated with sample availability and participant consent, is expected. Numbers of missing analyses will be provided along with numbers of participants included in the analysis, and tests conducted with and without successful outcomes.

If the date of the last IP exposure (ie, last ring removal) is incomplete or missing, the following imputation will be made:

- when only the day is missing, impute with min (last ring insertion date + 28 days, last day of the month), else
- impute with last ring insertion date + 28 days.

This should be added in a footnote in the applicable tables/listings. If the date itself should be printed, the original (not the imputed) date should be printed.

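### The Table 14.3.7.11 note gives a last ring with no removal date zero days of wear, which conflicts with SAP 6.6 and with the virology addendum and tilts the timing rows towards 'Before seroconversion'

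*SAP*

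**What the plan says.** Four places deal with missing ring or product dates.

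- **Main SAP, Appendix 1, Table 14.3.7.11.** This shell counts virology-population women by whether product use stopped at, after or before seroconversion. Its note says: "In case the date of last investigational product exposure (i.e. last ring removal) is missing, it is imputed with the last ring insertion date". Partial dates are not mentioned.
- **Main SAP 6.6.** After providing for adverse-event and concomitant-medication dates it says: "No other date imputations will be performed". The same section then makes one further exception, for a missing product start date: "the missing date will be imputed with the date of the enrollment visit". There is none for the stop date.
- **Virology addendum 4.4.** A fully missing last-removal date follows one rule: "impute with last ring insertion date + 28 days". A date that lacks only its day gets the earlier of that result and the month's end. On scope the section says only: "This should be added in a footnote in the applicable tables/listings". No output is named.
- **Main SAP, Listing 16.2.5.2.** For self-reported adherence only: "Missing or partial dates for when the ring was inserted or removed are treated as missing data during the calculation of the adherence rate".

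The footnotes to Tables 14.3.7.5 to 14.3.7.8, and the pregnancy rate in Table 14.3.7.4, compute person-years from the last removal date and give no rule for when it is missing. No text that I found ranks or reconciles these instructions.

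**The concern.** The insertion date is the earliest day on which a ring can have been removed. Using it as the removal date can therefore err in one direction only: exposure ends too soon. SAP 9.4.4 counts 30 days of expected wear from insertion, and protocol 6.1 describes a ring designed to release drug for at least a month, so zero days is the extreme choice.

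Table 14.3.7.11 exists to show when product use ended relative to seroconversion and first detectable HIV-1 RNA, as context for the resistance objective. A programmer who follows the note pushes affected women towards 'stopped before seroconversion'. One who follows 6.6 leaves them unclassified. The addendum, which aims to relate its findings to the genotyping in the main report, would give the same woman a different last-exposure date. Other outputs need that date too: the on-product and after-product rows of Table 14.3.7.12, the days since last ring exposure in Listing 16.2.8.15, and the person-years denominators.

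**Working it through.** The plan states no figure that depends on this rule, so there is nothing to reproduce. The check is date arithmetic.

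**Inputs.** Main note: removal = insertion + 0. Addendum 4.4: insertion + 28, or the earlier of that and month end when only the day is missing. Expected wear: 30 days (SAP 9.4.4), with ±7 days around it (SAP 9.2).

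**Step 1: fully missing date.** Let day 0 be the last insertion, and compare the imputed stop date with the seroconversion date.

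| Seroconversion, days after last insertion | Insertion-date rule | Insertion + 28 | Same class? |
|---|---|---|---|
| −1 | After | After | yes |
| 0 | At | After | no |
| 1 to 27 | Before | After | no |
| 28 | Before | At | no |
| 29 or later | Before | Before | yes |

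The rules disagree on 1 + 27 + 1 = 29 days. Example: inserted 10 March, seroconversion dated 24 March (day 14). The main note stops product on 10 March ('Before'); the addendum stops it on 7 April ('After'); 6.6 gives no class.

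**Step 2: only the day missing.** Inserted 10 March, removed on an unknown day in March: min(7 April, 31 March) = 31 March, which is insertion + 21. The main note does not cover this case.

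**Step 3: on-schedule visits.** If the visit falls 30 ± 7 days after the last insertion, that is days 23 to 37. The rules disagree on days 23 to 28 (6 of 15) and agree on 'Before' on days 29 to 37 (9 of 15), including nominal day 30.

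**Step 4: 28 or 30 days.** Insertion + 30 would differ from insertion + 28 on three days: day 28 (After against At), day 29 (After against Before) and day 30 (At against Before). The choice therefore matters at the nominal visit.

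**Step 5: product withheld at the positive visit.** Protocol 5.4.3 withholds product when both rapid tests are reactive and applies the last-product-use procedures, which include ring removal (protocol 4.4). In the example, if product was withheld on 24 March, insertion + 28 puts ring use 14 days past that visit. Capped at the visit, the class is 'At', which neither existing rule gives.

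**Step 6: person-years.** PY = (last removal − first insertion + 1) / 365.25. The two imputations differ by 28 / 365.25 = 0.077 PY per affected woman. The documents give no frequency of missing dates. Assuming 1,400 women with one year each and 1% to 20% missing:

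- 1%: 14 × 28 / 365.25 = 1.1 PY, or 0.08% of 1,400 PY
- 20%: 280 × 28 / 365.25 = 21.5 PY, or 1.5%

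With no imputation, each affected woman's whole PY is undefined: 14 to 280 PY under the same assumptions.

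**The case against.** The best defence is that little rides on the note. It sits under one descriptive table. The addendum is dated May 2021, calls its sequencing analysis exploratory and supplements a study report dated April 2020, so a different rule may be deliberate. Several stronger readings are tempting, and the documents do not support them.

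- A reader might infer that all affected women fall into 'Before'. They do not: seroconversion on the insertion day gives 'At', and an earlier one gives 'After'. Protocol 5.4.3 keeps some women with discordant tests on product, so the last insertion need not come first.
- A reader might infer that a woman is tabulated as off product in one place and on product in another. No addendum table has a stopped-before/after row. Membership of the addendum's virology population turns on seroconversion during product use and on HIV-1 RNA at enrolment and at the last product use visit. In the main SAP (9.3.1), the point of infection comes from reverse sequential PCR with investigator and sponsor-physician assessment. Neither text names the imputed date.
- A reader might infer that the adverse-event window, which runs "up to six weeks after last ring use", is shortened too. Nothing extends the note to SAP 10.1.1.
- A reader might infer that home ring changes make missing dates common. Protocol 6.4 places removal at the centre in visit months, and diary cards record dates for the additional rings (protocol 5.19). No frequency is given.

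All of these limits stand. They do not remove the contradiction with 6.6 or the one-sided error of the insertion-date rule. Nothing in either plan says that the different rule is intended.

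**Conclusion.** The point holds as a defect in a stated rule, with modest reach. The note contradicts SAP 6.6, differs from addendum 4.4, and is biased towards 'Before seroconversion' whenever seroconversion is dated after the last insertion. For a fully missing date, the disagreement with the addendum covers days 0 to 28 and no others.

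It touches descriptive rows for seroconverters without a last removal date. Their number is unknown; the addendum itself calls the numbers small, so one or two women could visibly move those rows. On-product infection status and the primary endpoints do not follow from it. The effect of +0 against +28 days on the overall rate is small under the assumptions shown; the larger gap is that the person-years formula has no rule at all. The plan should be changed because the rule is wrong as written and cheap to correct.

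One limit: addendum sections 2.1 and 2.2 and the end of the Table 14.3.7.9 shell through most of Table 14.3.7.10.1 were not available to me, so a reconciling sentence there cannot be excluded.

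**What to change.** Delete the note under Table 14.3.7.11. In SAP 6.6, add the last removal date to the listed exceptions, with one rule for fully missing and one for day-only-missing dates:

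- Base it on the expected wear period. The addendum's 28 days and the main SAP's 30 days must be reconciled first; the documents do not settle which applies.
- Cap the imputed date at the earliest of the visit at which product was recorded as withheld or discontinued, a reported ring loss, or last contact. For a day-only-missing date, also cap at the end of the known month.
- Apply it to the person-years formula (Tables 14.3.7.4 to 14.3.7.8), Tables 14.3.7.11 and 14.3.7.12, Listing 16.2.8.15 and the addendum, and name those outputs.
- Flag women with an imputed date, and show the insertion-date version of Table 14.3.7.11 as a sensitivity row.

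The cost is a short paragraph in 6.6, one deleted note, a cross-reference in the addendum, one flag and one extra row. Because the study report is already dated 9 April 2020, acting on it would also mean a corrected or footnoted table there. No new data are needed.
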